3.1.3 Trial Schedule

The estimated first subject, first visit is Q3 2018 with last subject, last visit during Q3 2019.

3.2 Planned Number of Trial Sites and Subjects

Approximately 240 subjects will be needed to complete the controlled ovarian stimulation cycle, undergo oocyte retrieval, be treated with PVR, and receive fresh embryo transfer.

3.3 Interim Analysis

No interim analysis is planned.

3.4 Data Monitoring Committee (DMC)

No data monitoring committee is planned.

3.5 Discussion of Overall Trial Design and Choice of Control Groups

3.5.1 Trial Design

This is an open-label, single-arm trial of progesterone supplementation (luteal phase support) in women undergoing IVF with fresh oocytes. Each trial center will follow the trial center's standard practice for ART unless otherwise noted in this protocol. On the day after oocyte retrieval, the subject will begin treatment with the IMP, PVR. Embryo transfer will occur 5 days after oocyte retrieval. A serum pregnancy test will be conducted 2 weeks after the oocyte retrieval. Subjects with a β -hCG level <5 mIU/mL will be discontinued from the trial. Those with a β -hCG level ≥ 5 mIU/mL will continue dosing with PVR for up to a total of 10 weeks.

The primary objective is to estimate the cumulative rate of any spontaneous abortion, including spontaneous clinically recognized pregnancy loss and blighted ovum during the trial (up to Week 12 following oocyte retrieval), in subjects treated with PVR following fresh embryo transfer. Approximately 240 subjects will be enrolled in the trial in order to ensure that 215 subjects undergo fresh embryo transfer.

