Consent and Screening	Down-regulation	Visits 1 and 2	Visit 3	Visits 4-9: Day after oocyte retrieval and ongoing pregnancy (~10 weeks) PVR1 through PVR10	Visit 10: End-of-trial visit (2 weeks after last exposure to Investigational Medicinal Product)

NUMBER OF SUBJECTS

Approximately 240 subjects will be needed to complete the controlled ovarian stimulation cycle, undergo oocyte retrieval, be treated with PVR, and receive fresh embryo transfer.

CRITERIA FOR INCLUSION / EXCLUSION

Inclusion Criteria

Subjects must meet the following inclusion criteria:

1. Informed consent signed and dated prior to any trial related procedures.
2. Pre-menopausal females aged 18-34 years old at time of consent.
3. Documentation of a normal uterine cavity by hysteroscopy, hydrosonogram, or hysterosalpingogram within 1 year of screening.
4. Documentation of normal Pap smear test within 24 months of screening.

5. Documentation of negative testing within 6 months of the start of screening for serum Hepatitis B surface antigen, Hepatitis C antibody, human immunodeficiency virus antibody, rapid plasma reagin/venereal disease research laboratory.
6. Documentation of rubella antibody, ABO grouping, Rho typing, and normal prolactin and thyroid function within 6 months of screening.
7. At least 1 cycle without reproductive hormone medication prior to the screening follicle stimulating hormone (FSH) and estradiol blood draw.
8. Tubal, idiopathic, male factor, ovulatory dysfunction, or endometriosis-linked infertility.
9. For fresh sperm: sperm assessed for leukospermia (≥ 2 million white blood cells/mL or round cells/mL) is required within 2 months of pituitary down regulation OR male partner empirically treated with antibiotics prior to the IVF cycle.
10. Semen analysis within 1 year of screening by standard World Health Organization and/or Kruger criteria. Frozen sperm, including donor sperm, may be used, as long as testing done at the time of freezing meets standard criteria. Male partners with obstructive azoospermia will not be required to have this semen analysis.
11. Able to understand, read, and sign an informed consent after the nature of the trial has been fully explained.
12. Able to complete all trial procedures.

Exclusion Criteria

The presence of any of the following excludes a subject from trial enrollment:

1. Contraindications to the use of progesterone, which include:
 - Known sensitivity to progesterone or related drugs
 - Undiagnosed vaginal bleeding

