4.4 Withdrawal Criteria

Withdrawal from Trial

Every subject has the right to withdraw from the trial at any time for any reason, without the need to justify their decision. A subject's participation is to terminate immediately upon her request. However, the Investigator should record the reason for the subject's withdrawal, if possible.

If, at the time of discontinuation, a dose of the IMP has already been administered, the subject must be advised to consider follow-up safety investigations, which will include all procedures outlined for the Early Withdrawal Visit (section [6.3.8](#)).

The subject can also be withdrawn from the trial at any time at the discretion of the Investigator; the reason should be discussed with the Sponsor prior to discontinuation. For any discontinuation, the Investigator will obtain all the required details and document the date of the premature termination and the main reason in the source documents and eCRF.

A subject who withdraws from the trial after embryo transfer will not be replaced.

Withdrawal of Consent

If the subject withdraws her consent, data collected up to withdrawal will remain in the database, but no further data will be collected. Samples and recordings obtained before withdrawal may be analyzed. This will be described in the Informed Consent Documents. The subject can request destruction of samples which would otherwise have been kept in storage.

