240	93.1%	81.8%	63.2%
365	98.9%	94.2%	80.9%

mITT = modified intention-to-treat

Taking the middle of this range, a trial with 240 subjects in the mITT analysis population is considered as being adequately powered under a relevant assumption in the target population. Full simulation code is provided in [Appendix 6](#).

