9.5 Analysis Sets

9.5.1 mITT Cohort

The mITT cohort consists of all subjects who had successful oocyte retrieval, received at least 1 dose of IMP, and had completed fresh embryo transfer.

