The planned sample size is based only on subjects that undergo fresh embryo transfer. No further drop-outs are assumed. The analysis is evaluated across a range of true effects for the current trial's spontaneous abortion rate. For the null scenario where in truth the PVR spontaneous abortion rate is 15%, 100,000 sets of trials were simulated. For all other assumed scenarios, 5,000 sets of trials were simulated.

Overall Success

We evaluated the overall probability that the 95% credible interval is entirely below 15% for each scenario of the true PVR rate. If PVR truly maintains an abortion rate below 15%, then this represents the power for achieving a credible interval entirely below 15%. If the true rate of abortions for PVR is 15%, then obtaining a credible interval entirely below 15% is the type I error. Results are provided in the table below.

True PVR Rate	8%	9%	10%	11%	12%	13%	14%	15%
Trial Success	0.979	0.933	0.830	0.670	0.485	0.297	0.167	0.084

When in truth the PVR spontaneous abortion rate is 9%, the trial has 93.3% power of achieving a 95% credible interval entirely below 15%. Alternatively, when in truth the spontaneous abortion rate is 15%, the trial has a 8.4% rate of success.

Inference Associated with Various Observed Rates

For various observed rates of spontaneous abortions, the corresponding primary analysis based on the hierarchical model is described below. The posterior mean, 95% credible interval, effective number of borrowed subjects, and the borrowing percentage (out of the n=549 subjects from the previous trial) is provided. The effective number of borrowed subjects calculation $[E(\pi_1)*(1-E(\pi_1))/Var(\pi_1)-1-240]$ is somewhat approximate as it is based on the binomial likelihood. Results are provided in the below table.

Observed Data	Estimated Rate (%) (95% CI)	Effective Number of Borrowed Subjects	Borrowing Percentage
19/240 (7.92%)	8.6% (5.7, 11.7)	103	18.9%
24/240 (10.00%)	10.0% (7.2, 13.3)	130	23.7%
36/240 (15.00%)	13.8% (10.1, 18.5)	9	1.7%

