Borrowing based on the hierarchical modeling is dynamic, with higher borrowing achieved when the current trial's results are similar to the previous data and minimal borrowing when the current trial's results are at 15%. This is evidenced by both the decreasing number of borrowed subjects and the increasing width of the credible intervals. Also, based on 240 subjects being included in the analysis, the maximal number of observed responses which maintains a 95% credible interval entirely below 15% is 28.

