**Table 2 Power Achieved over Varying Sample Sizes and Assumed Spontaneous Abortion Rates**

Required Sample Size (mITT Analysis Population)	Assumed “True” Spontaneous Abortion Rate		
	8%	9%	10%
180	80.3%	64.8%	46.1%
240	93.1%	81.8%	63.2%
365	98.9%	94.2%	80.9%

Taking the middle of this range, a trial with 240 subjects in the mITT analysis population is considered as being adequately powered under a relevant assumption in the target population. Full simulation code is provided in [Appendix 2](#).

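### Protocol 3.5.1 plans 240 enrolled for 215 fresh transfers, but the sample size and power elsewhere require 240 with fresh transfer

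*Protocol*

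**What the plan says.** Protocol 3.5.1 (Trial Design) says: "Approximately 240 subjects will be enrolled in the trial in order to ensure that 215 subjects undergo fresh embryo transfer". There, 240 is the number enrolled and 215 the number with transfer.

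Every other statement of the target ties 240 to transferred or analysed subjects:

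- **Protocol synopsis (Number of Subjects) and 3.2:** "Approximately 240 subjects will be needed to complete the controlled ovarian stimulation cycle, undergo oocyte retrieval, be treated with PVR, and receive fresh embryo transfer".
- **Protocol 9.2:** "Taking the middle of this range, a trial with 240 subjects in the mITT analysis population is considered as being adequately powered". SAP 3.3 agrees: "a trial with 240 subjects in the mITT analysis population is considered as being adequately powered under a relevant assumption in the target population".
- **Protocol Appendix 6, Operating Characteristics (repeated in SAP Appendix 2):** "The planned sample size is based only on subjects that undergo fresh embryo transfer. No further drop-outs are assumed". The illustrations that follow are "based on 240 subjects being included in the analysis".

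The link between transfer and analysis is the cohort definition in Protocol 9.5.1 and SAP 6.1: "The mITT cohort consists of all subjects who had successful oocyte retrieval, received at least 1 dose of IMP, and had completed fresh embryo transfer". Hence the size of the mITT set cannot exceed the number of completed fresh transfers.

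**The concern.** The figure 215 occurs only in Protocol 3.5.1. No power is given for it, and no text explains how it relates to 240. Nor is it said whether enrolment means consent, start of suppression, or retrieval.

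Reading 240 as approximate does not help, because 3.5.1 itself separates enrolled from transferred subjects and gives each its own number. Nor can a loss of 25 subjects be hidden inside the 240: Appendix 6 counts only transferred subjects and assumes no loss after that.

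At stake is the size of the primary analysis set and whether the stated power applies to it. A reader of 3.5.1 could regard recruitment as complete at 240 enrolled and expect about 215 in the mITT cohort. No interim analysis or data monitoring committee is planned (Protocol 3.3, 3.4), so neither would bring a shortfall to light.

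**Working it through.** **Inputs**

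| Input | Value | Source |
|---|---|---|
| Success rule | upper limit of two-sided exact 95% CI below 0.15 | Protocol 9.1, 9.2; SAP 9.3.1 |
| Target power | 80% | Protocol 9.2; SAP 3.3 |
| Assumed true rates | 8%, 9%, 10% | Protocol Table 9-1; SAP Table 2 |
| mITT size supporting the power claim | 240 | Protocol 9.2; SAP 3.3 |
| Transfers under 3.5.1 | 215 | Protocol 3.5.1 |

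**Formulas.** This is the exact counterpart of the simulation in Appendix 6. For x events in n subjects, the Clopper-Pearson upper limit U(x, n) is the 0.975 quantile of Beta(x + 1, n − x). Let c be the largest x with U(x, n) < 0.15. Power is P(X ≤ c) for X ~ Binomial(n, p).

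**Step 1: reproduce the plan's figures**

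| n | p = 8%, printed / exact | p = 9%, printed / exact | p = 10%, printed / exact |
|---|---|---|---|
| 180 | 80.3 / 80.6 | 64.8 / 64.4 | 46.1 / 46.4 |
| 240 | 93.1 / 92.8 | 81.8 / 81.3 | 63.2 / 63.6 |
| 365 | 98.9 / 98.8 | 94.2 / 93.9 | 80.9 / 81.0 |

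Every cell agrees to within about half a point. The table is correct for the sizes it names.

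**Step 2: apply the same rule to both targets**

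| n | c | c/n | U(c, n) | U(c+1, n) | Power at 8% | 9% | 10% |
|---|---|---|---|---|---|---|---|
| 240 | 25 | 10.4% | 0.1499 | 0.1547 | 92.8% | 81.3% | 63.6% |
| 215 | 21 | 9.8% | 0.1454 | 0.1508 | 85.9% | 70.4% | 51.2% |

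The loss at 9% is 81.3 − 70.4 = 10.9 points. Only at 9% does the choice of target decide whether 80% is reached: at 8% both exceed it, and at 10% both fall short.

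**Step 3: allow for the saw-tooth.** Exact power rises when c steps up and falls as n grows at fixed c. At n = 240 it is on a peak; at n = 215 it is close to a trough. At 9%:

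- Peak to peak: n = 217 (c = 22) gives 76.5% and n = 240 gives 81.3%, a loss of 4.8 points.
- Trough to trough: n = 216 (c = 21) gives 69.6% and n = 239 (c = 24) gives 75.6%, a loss of 6.0 points.
- No n from 215 to 239 reaches 80%. The maximum is 79.4%, at n = 233.

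**Step 4: the enrolment 3.5.1 would imply for 240 transfers.** If its ratio held (an assumption), retention is 215/240 = 89.6%. Then 240 transfers need 240/0.8958 = 267.9, so about 268 enrolled. The documents state no such number.

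**The case against.** The strongest reply concerns weight. It is one sentence in a design discussion, while the sections that set the sample size agree on 240 and the SAP never mentions 215. The likely repair is therefore textual. In addition:

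- The primary objective is to estimate a rate, and Protocol 2 and SAP 2 decline to tie the trial's success to it. The exact interval is valid at any n. At a 9% rate the approximate (Wald) half-width, 1.96 × √(0.09 × 0.91 / n), is 3.6 points at 240 and 3.8 at 215.
- Crossing 80% is fragile even around 240. Power at 9% is 75.6% at n = 239 and 77.1% to 79.5% for n = 243 to 247.
- No calculation in the plan is wrong; this is an inconsistency between sections.

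All of that stands, and it limits the consequence. It does not remove the contradiction: the comparison with 15% remains prespecified, and the plan justifies its size by that comparison.

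Protocol 4.4 ("A subject who withdraws from the trial after embryo transfer will not be replaced") might suggest that recruitment counts transfers, but it fits either target and settles nothing.

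**Conclusion.** The concern holds. Protocol 3.5.1 conflicts with the synopsis, Protocol 3.2, 9.2 and Appendix 6, and SAP 3.3 and Appendix 2. The printed 81.8% at a 9% rate applies to 240 mITT subjects and does not carry over to 215, where the exact figure is 70.4%. About 5 to 6 of the 10.9 points reflect the smaller sample; the rest comes from where 215 and 240 fall on the saw-tooth.

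These figures assume the plan's binomial model, its two-sided 95% exact interval, and a mITT set equal to the number of transfers. The power loss would be real only if 3.5.1 were the working target, which nothing in the documents shows. The result is an internally inconsistent sample size, neither a wrong power table nor a failed trial. It still needs correcting, because it concerns the size of the primary analysis set.

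**What to change.** **If 240 transfers is the target**, as every other section says, rewrite the sentence in Protocol 3.5.1 so that about 240 subjects undergo fresh transfer and form the mITT cohort. Give the enrolment number separately, define the point at which a subject counts as enrolled, and state the assumed loss before transfer. This adds no subjects to the 240 already planned for transfer.

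**If 215 transfers is the target**, change the synopsis, Protocol 3.2, 9.2 and Appendix 6, and SAP 3.3 and Appendix 2 to 215. Restate power as about 86%, 70% and 51% at 8%, 9% and 10%, and rerun the Appendix 6 and SAP Appendix 2 operating characteristics that assume 240. No extra subjects are needed, but the claim of adequate power at 9% goes.

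If recruitment has been working to 215 and the stated power is to be kept, 240 − 215 = 25 more subjects with transfer are needed.

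The estimator, the mITT definition and the 15% comparison do not change under any of these.

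A separate, minor point: Protocol 9.7.2 prints 55/549 as 10.2%, but 55/549 = 10.0% (56/549 and 55/539 both give 10.2%). Check the count against the earlier study's source before running the sensitivity model, which uses the count.

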3.5.2 Selection of Endpoints

The endpoints in this trial (rate of any spontaneous abortion, biochemical abortion, ectopic and heterotopic pregnancies as well as rate of clinical pregnancy and positive β -hCG) are typical endpoints to demonstrate the safety of products used for progesterone supplementation in women undergoing ART. AEs of special interest due to the vaginal administration are also included as secondary endpoints, and cover vaginal bleeding/spotting, vaginal hemorrhage, pain, vaginal

infection, vaginal irritation, vaginal and cervical abrasions and lesions, and vaginal adhesions. Finally, typical safety endpoints such as laboratory results and vital signs are also included.

3.5.3 Blinding

This is an open-label trial.

3.5.4 Selection of Doses in the Trial

Subjects will be instructed to insert the first PVR on the day after oocyte retrieval, which contains 11 mg progesterone/day and remains in place a minimum of 23 hours/day for 7 days.

3.5.5 Selection and Timing of Dose for Each Subject

A new PVR will be inserted every 7 days, with up to 10 PVRs used through Week 12 of pregnancy (10 weeks post-oocyte retrieval).

3.5.6 Discontinuation and Trial Stopping Criteria

Discontinuation Criteria

Two days prior to oocyte retrieval, a TVUS will be performed to assess follicle size. A subject must have at least 2 follicles ≥ 17 mm (mean of 2 dimensions) to receive the hCG trigger. Subjects who do not reach this threshold after 20 days of stimulation are to be discontinued from the trial. If the estradiol level is ≥ 5000 pg/mL, hCG should not be administered and the subject should be discontinued from the trial.

A serum pregnancy test will be conducted 2, 2.5, and 3 weeks after the oocyte retrieval. Subjects with a β -hCG level < 5 mIU/mL will be discontinued from the trial. A TVUS will be performed to document the presence of an intrauterine gestational sac 4.5 weeks after oocyte retrieval. If it is determined that the subject has an ectopic pregnancy, the subject will be treated according to the site's standard protocol and will be withdrawn from the trial.

Subjects who discontinue the trial are to complete an Early Withdrawal Visit (section [6.3.8](#)) no later than 1 week after the last dose of the IMP. An End of Trial Visit (section [6.4](#)) is required 2 weeks after the last dose of IMP.

Trial Stopping Criteria

Occurrence of the following may warrant consideration of trial termination:

Life-threatening SAEs with suspected causality to the IMP, but not limited to those with grade 4 as detailed in [Appendix 2](#) and [Appendix 3](#).

Ferring's internal Safety Committee will review each occurrence and provide a recommendation as to whether to discontinue the trial. The responsibilities and composition of the internal Safety Committee are provided in a separate charter document, available before the first subject's first visit.

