2.2 Endpoints

Primary Endpoint

- Cumulative rate of any spontaneous abortion occurring on or before 12 weeks following oocyte retrieval in all subjects treated with PVR and undergoing fresh embryo transfer.
Note: spontaneous abortion is defined as two positive β -hCG tests occurring at least two days apart on or after 2 weeks post-oocyte retrieval, but followed by observation of any empty intrauterine gestational sac (blighted ovum), intrauterine gestation without a fetal heart beat, or absence of viable fetuses, as documented by transvaginal ultrasound (TVUS).

Secondary Endpoints

- Cumulative rate of spontaneous abortions determined at 6 and 10 weeks post-oocyte retrieval in all subjects treated with PVR.
- Cumulative rate of biochemical abortions determined at 6 and 10 weeks post-oocyte retrieval in all subjects treated with PVR. Biochemical abortion is defined as a positive β -hCG test at 2 weeks and 2 weeks + 3-4 days post-oocyte retrieval, but followed by no observed gestational sac on a later TVUS, or followed by a negative β -hCG test.
- Rate of ectopic and heterotopic pregnancies in all subjects treated with PVR following oocyte retrieval.
- Rate of abnormal findings in clinical laboratory tests and vital signs for all subjects treated with PVR.
- Frequency, intensity/grade, seriousness, and relatedness of adverse events (AEs) for all subjects treated with PVR.
- Frequency, intensity/grade of vaginal bleeding/spotting, vaginal hemorrhage, pain, vaginal infection, and vaginal irritation for all subjects treated with PVR.
- Frequency, intensity/grade, seriousness, and relatedness of AEs associated with vaginal and cervical abrasions and lesions and with vaginal adhesions for all subjects treated with PVR.
- Frequency and reason for PVR discontinuation.
- Positive β -hCG rate (positive serum β -hCG test) at 2 weeks and 2 weeks + 3-4 days post-oocyte retrieval in all subjects treated with PVR.
- Clinical pregnancy rate (TVUS showing at least 1 intrauterine gestational sac with fetal heart beat) at 6 and 10 weeks post-oocyte retrieval in all subjects treated with PVR.

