3.5.7 Follow-up Procedures

Two weeks after the last exposure to the IMP, subjects will return for an End-of-trial Visit. Physical and pelvic examinations will be performed; vital signs will be measured; blood and urine will be collected for hematology, chemistry and urinalysis; and AEs will be assessed. If any lesions or abrasions are found on the cervix or vagina or vaginal adhesions are noted, another examination will be performed 2-4 days later until the lesions/abrasions or vaginal adhesions resolve or until the final assessment at the End-of-trial visit, whichever comes first. Vaginal adhesions observed can be surgically addressed based on the Investigator's judgement.

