6.4 End-of-trial

The End-of-trial visit (Visit 10) occurs 12 weeks (84 ± 2 days) after oocyte retrieval (week 14 of pregnancy) / 2 weeks (14 ± 2 days) after the last exposure to IMP.

The following end-of-trial procedures / assessments must take place:

- Vital signs

- Blood collection for assessment of:
 - Clinical chemistry and hematology parameters
- Urinalysis
- Complete physical examination (including weight, and BMI calculation)
- Pelvic examination (documentation of presence and grade [intensity] of any pain, irritation, abrasions, or lesions on the cervix or vagina or vaginal adhesions).
If any lesions or abrasions are found on the cervix or vagina or vaginal adhesions are noted, another examination will be performed 2-4 days later.
- TVUS or abdominal ultrasound (pregnant subjects only) to determine the number of gestational sacs with/without fetal heart beat and estimate gestational age
- Recording of any vaginal bleeding noted in the subject's bleeding log since the previous visit
- Assessment of vaginal hemorrhage
- Recording of use of any concomitant medication
- Recording of AEs

After completion of the End-of-trial visit, subjects will be referred to their obstetricians for further care.

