7.2.9 Adverse Events

AEs will be recorded from the signed informed consent for participation in the trial at screening until the End-of-trial visit (Visit 10).

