8.5.2 Follow-up of Adverse Events on Non-Investigational Medicinal Products During the Trial

In case an AE is recognised as an adverse drug reaction caused by a concomitant NIMP, investigators should report to each Marketing Authorisation Holder. For adverse drug reactions caused by an NIMP where Ferring is the Marketing Authorisation Holder, the case will have to be reported to Ferring.

8.5.3 Collection of Serious Adverse Events with Onset after Last Visit in the Trial

If an Investigator becomes aware of an SAE after the subject's last visit, and he/she assesses the SAE to have a reasonable possible causality to the IMP, the case will have to be reported to Ferring, regardless of how long after the end of the trial this takes place.

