## 6 Analysis sets

### 6.1 Modified Intention-To-Treat (mITT) Cohort

The mITT cohort consists of all subjects who had successful oocyte retrieval, received at least 1 dose of IMP, and had completed fresh embryo transfer.

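### A woman who stops the ring while pregnant is last assessed 2 weeks later, so a loss after that and before Week 12 counts as a non-event in the primary safety rate

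*Protocol*

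**What the plan says.** **Endpoint window.** Protocol 2.2 counts losses "on or before 12 weeks following oocyte retrieval in all subjects treated with PVR and undergoing fresh embryo transfer". SAP 9.3.1 analyses the same window in the mITT cohort and compares the upper limit of the two-sided exact 95% interval with 15%.

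**Last visit.** Protocol 3.5.6 requires an Early Withdrawal Visit within 1 week of the last dose for women who discontinue the trial, and adds that an End of Trial Visit "is required 2 weeks after the last dose of IMP". Protocol 3.5.7 says of subjects generally: "Two weeks after the last exposure to the IMP, subjects will return for an End-of-trial Visit". Protocol 6.4 gives one visit two anchors: 12 weeks (84 ± 2 days) "after oocyte retrieval (week 14 of pregnancy) / 2 weeks" (14 ± 2 days) after last exposure.

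**Collection after that visit.** Under Protocol 7.2.9, AE recording ends at the End-of-trial visit. Under Protocol 8.5.3, an SAE that the investigator learns of later is reportable only if "he/she assesses the SAE to have a reasonable possible causality to the IMP".

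**Denominator and numerator.** The mITT cohort (SAP 6.1) is every woman with successful retrieval who "received at least 1 dose of IMP, and had completed fresh embryo transfer". It has no follow-up condition. Protocol 4.4 adds: "A subject who withdraws from the trial after embryo transfer will not be replaced". SAP 9.2 counts a loss only from an ultrasound finding or a recorded AE. SAP 9.2 and 9.3 say nothing about an unknown outcome, whereas SAP 9.4.4 and 9.4.5 state how missing data are handled for positive β-hCG and 6-week clinical pregnancy.

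**The concern.** The two anchors in Protocol 6.4 coincide only for women who use rings for about 10 weeks. For a woman who stops earlier while still pregnant, the endpoint window stays open after her last planned assessment. A loss in that interval leaves no ultrasound and, as a rule, no AE record, yet she remains in the denominator.

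Women withdrawn for a negative β-hCG, an ectopic pregnancy or a confirmed loss are not affected, because their outcome is known. The issue is the woman who leaves for another reason, such as an AE, her own choice or the investigator's decision, with a continuing pregnancy. The plan expects such women: ring discontinuation is a secondary endpoint, and SAP 10.4.1 has a bleeding-log rule for early stoppers. The operating characteristics in SAP Appendix 2 nevertheless assume no drop-out after transfer.

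This is the primary safety rate, and the error from this source runs one way, towards fewer losses. As planned, a reader of the 15% comparison could not tell how many Week 12 outcomes were unknown or whether they could change the conclusion. The Bayesian sensitivity analysis uses the same event count, so it would not reveal the problem.

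**Working it through.** **1. The plan's own figures.** Inputs are n = 240, the 15% threshold and the exact 95% interval (Protocol 9.2, SAP 3.3). The Clopper-Pearson upper limit for x losses is the 0.975 quantile of Beta(x + 1, n − x).

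| Losses of 240 | Upper limit |
|---|---|
| 22 | 13.55% |
| 24 | 14.51% |
| 25 | 14.99% |
| 26 | 15.47% |
| 27 | 15.94% |

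The interval excludes 15% when x ≤ 25. Power at a true 9% is P(X ≤ 25 | 240, 0.09) = 81.3%, against the simulated 81.8% in the plan. The other eight cells of the power table also agree within simulation error, so the sample-size arithmetic is not in question.

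**2. Length of the gap.** Uncovered time is 12 − (week of last exposure + 2).
- Last exposure at Week 4: 12 − 6 = about 6 weeks.
- Week 6: 12 − 8 = about 4 weeks.
- Week 8: 12 − 10 = about 2 weeks.

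**3. Effect on false exclusion.** Suppose the true rate is 15%, k of the 240 women leave while pregnant, and each has probability r of a later unseen loss. The observable rate is 0.15 − k·r/240, and false exclusion is P(X ≤ 25 | 240, 0.15 − k·r/240). Neither k nor r is in the documents; both are assumptions.

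| k | r = 10% | r = 20% | r = 30% |
|---|---|---|---|
| 0 | 2.5% | 2.5% | 2.5% |
| 2 | 2.7% | 2.9% | 3.2% |
| 5 | 3.0% | 3.7% | 4.5% |
| 12 | 4.0% | 6.2% | 9.3% |

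**4. Tipping points.** The number of unseen losses that reverses a pass is 26 − x: 4 at 22 observed losses, 2 at 24, and 1 at 25. With 22 observed and 5 unknown, reversal needs at least 4 losses among 5. That probability is 0.05%, 0.7% or 3.1% at r = 10%, 20% or 30%.

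**5. Cost of the extreme bound.** Let a share q of women be unknown, all counted as losses, with a true rate of 9%. If they would otherwise lose at 9%, the rate becomes 0.09(1 − q) + q. If none would otherwise be a loss, it becomes 0.09 + q. The chance of excluding 15% falls from 81.3% to 65.4% or 63.6% at q = 1%, and to 47.2% or 43.7% at q = 2%.

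**The case against.** The strongest reply has four parts.

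- **Coverage is better than it looks.** She has an ultrasound at both the Early-withdrawal and End-of-trial visits if pregnant, and AEs feed the endpoint up to the second. Protocol 8.5.1 also requires continued follow-up of serious or possibly related AEs after the last visit, so a qualifying threatened-abortion AE already open would be pursued. This stands, but 8.5.1 covers only events that began during the trial. It does not find a new loss.
- **The text can be read otherwise.** Protocol 6.4 names 84 days first, and the objective speaks of losses during the trial. But that phrase is itself explained as up to Week 12, and 3.5.6 is explicit for women who discontinue. SAP 10.4.1 also treats stopping the ring early as leading to the Early Withdrawal Visit. At best the anchors conflict.
- **SAP 9.2 is already a full derivation.** A woman who meets no condition is a non-event, and the rules in SAP 9.4.4 and 9.4.5 also score missing as no event unless later evidence shows otherwise. This is fair: copying them would not help. For a safety endpoint, however, that default is the favourable one, and nothing tests it.
- **The effect may be small.** Few women may leave while pregnant, and at a 5% later-loss risk with 5 such women false exclusion is only 2.7%. Discontinuations are tabulated by reason, and Protocol 2 says that success is not tied to this endpoint. All of this stands. It limits the weight of the point, but the tabulation is not split by pregnancy status and so does not give the number of unknown outcomes.

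**Conclusion.** The concern holds. Followed as written, the plan scores a loss after an early stopper's last visit as no spontaneous abortion. No sentence says so. It follows from a fixed denominator, a numerator that needs an observed or recorded loss, and follow-up tied to the last ring. The direction of this component is certain: it lowers the observed rate. The net direction of all the endpoint rules together is not claimed.

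The size is unknown because it depends on two assumed quantities, the number of women who leave while pregnant and their later risk of loss. Under the ranges shown, false exclusion at a true 15% stays close to 2.5% with 2 such women and reaches 9.3% only with 12 women at 30% risk. The gap matters mainly when the count is near 25 of 240. It should be fixed because the remedy is cheap and this is the primary safety rate, but it does not undermine the design.

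**What to change.** 1. **Protocol 3.5.6, 3.5.7, 4.4 and 6.4:** reconcile the two anchors. Keep the safety visit tied to the last ring, and separately obtain pregnancy status at 12 weeks after retrieval for every mITT woman who is pregnant when she stops the ring or leaves. A visit, telephone call or obstetric record would do. Women who withdraw consent to further data collection are excepted under Protocol 4.4.
2. **SAP 9.3.1:** define an unknown Week 12 outcome as pregnant at last assessment, no confirmed loss, and no pregnancy status within or after the Visit 10 window. Report the number of such women beside the primary result.
3. **Supporting analysis:** tabulate the exact upper limit for x + j losses, with j from 0 to the number unknown, and mark the smallest j at which it reaches 15%. Counting all unknowns as losses is the extreme row.
4. **Optional:** a cumulative-incidence estimate that censors unknowns at last contact and treats negative β-hCG, biochemical abortion and ectopic pregnancy as competing outcomes.

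The primary analysis and all treatment rules stay as they are. The all-unknown-as-loss bound should not become primary, given the loss of power shown in step 5 of the working. The cost is wording in both documents, a few contacts or record checks, and one or two supporting outputs. Women who withdraw consent will remain unknown.
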